#### **2.4.4 Pre-index characteristics**

The index visit functions as a baseline to the extent that patients will be described / stratified according to characteristics that were documented at the beginning of the index visit, prior to potential intervention exposure. Patient information documented in the EHR or health plan claims databases on or prior to the index visit will be used to describe pre-intervention patient characteristics (e.g., age on index date, sex, risk of CI diagnosis at index visit), organize patients into groups to assess treatment heterogeneity (e.g., insurance status) or calculate pre-index values (e.g., healthcare utilization in pre-index year). All metrics needed for baseline characterization or reference are either already available in historical databases or will be documented in the course of care delivery. None will be assessed solely for research purposes.

#### **2.4.5 Use of EHR and administrative data sources**

Outcomes that assess clinical effectiveness, cost, utilization and safety will be calculated using data extracted from EHR and administrative data sources maintained by HealthPartners. By using these data sources, outcomes can be ascertained identically for all accrued patients in all randomized clinics. Also, documentation will occur in the course of delivering health care or administering health insurance (cost outcomes) so that records should be reasonably accurate and complete with minimal (and randomly) missing information. When care is delivered outside the HealthPartners care system, health care claims can document their occurrence for patients who are also health plan members. Missing information due to events for which patients do not seek care or care that escapes documentation in the EHR or claims will be assumed to occur equally across treatment groups.

### **3.0 ANALYSIS PLAN**

#### **3.1 Reporting and descriptive analyses**

The number of patients accrued into the study will be monitored over the course of the accrual period by treatment arm, clinic and key patient characteristics (e.g., age, reason for eligibility). The number of index visits in CI-CDS clinics when a front-end user opens the CI-CDS interface

or prints CI-CDS content will also be monitored. Anomalous accrual counts or use rates will prompt investigation to ensure proper algorithm function.

Demographic and clinical patient characteristics that were available in the EHR at or prior to the index visit will be summarized for all patients in the ITT population, overall and by treatment arm. Patient characteristics related to the risk of CI or its diagnosis (e.g., age, sex, comorbidities) that are imbalanced across treatment arms may be considered for inclusion as covariates in secondary analyses. Pre-intervention characteristics will also be used as moderators in planned heterogeneity of treatment analyses.

Intervention exposure will be quantified by counting CI-CDS eligible visits through the end of each patient's observation period, and documenting CI-CDS use at those visits. Eligibility and exposure will be calculated and summarized, overall and by treatment arm.

A flow diagram will be assembled that follows the recommendations put forth in the extended Consolidated Standards of Reporting Trials (CONSORT) statement that applies to cluster randomized trials. The CONSORT figure will summarize the number of clinics and patients screened for eligibility and reasons for ineligibility; the allocation of clinics and patients to treatment arm; the range of patients per clinic by arm; intervention exposure at index and post-index visits by arm; and analyzed sample size with reasons for exclusions by arm.

### 3.2 Primary effectiveness analysis

The H1 effectiveness analyses – comparing likelihood of CI recognition across treatment arms – will be carried out using the ITT sample data: patients accrued from CI-CDS and UC clinics who are at elevated risk for CI but without a CI diagnosis prior to their index visit and not on a research exclusion list. Descriptive statistics will be used to characterize, overall and by treatment arm, the proportion of ITT sample patients who have CI recognized during the observation period, the time elapsed between study accrual and recognition and the clinic intraclass correlation in CI recognition. H1 will be tested using a generalized linear mixed model (LMM) to account for clustering within randomized clinics and normalize the binary outcome via a distribution-appropriate link function (e.g., logit, log). The model will include fixed effects for clinic-randomized treatment group and any patient covariates (e.g., age, sex, predicted risk score) and a random clinic intercept:

$$\text{logit}(\text{diagnosis}_{ji}) = \gamma_{00} + \gamma_{10}\text{CI-CDS}_j + \gamma_{0*}(\text{pt covars})_{ji} + [v_j], \quad \text{where } j=\text{clinic, } i=\text{patient.}$$

Parameter  $\gamma_{10}$  is expected to be positive and statistically significant, indicating that patients in clinics randomly assigned to CI-CDS are more likely to receive a CI diagnosis in the observation period than patients in UC clinics. Model-estimated outcomes will be calculated by treatment group, and the treatment effect will be presented as an odds ratio (OR, or risk ratio [RR]) and its 95% confidence interval.

A secondary model will add a fixed coefficient that represents time elapsed between the index visit and the first EHR-documented CI diagnosis, or zero for those lacking a CI diagnosis, and the interaction between treatment group and time. The time covariate will be coded as (days since index)/365 so that it quantifies the predicted annual change in CI diagnosis rates. The time parameter is expected to be near zero and not statistically significant. Should the time elapsed between index and CI diagnosis differ by treatment group, log (observation time) may be included as an offset in the primary analysis.

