9.5 Data Analyses

9.5.1 Primary analysis

The H1 sample will consist of primary effectiveness site patients accrued from the CI-CDS and UC clinics who are at elevated risk for CI but without a CI diagnosis at index. The primary outcome is defined as at least one CI diagnostic code or CI diagnosis entry on the problem list at any time between the index visit and the end of the observation period (at least 12 and up to 24 months post-index), inclusive. H1 will be tested using a generalized linear mixed model (LMM) to account for clustering within randomized clinics and normalize the binary outcome via a distribution-appropriate link function (e.g., logit, log). Clinic-randomized treatment group and any patient covariates (e.g., age at index visit, sex, MC-PLUS risk score at index visit) will be treated as fixed effects.

Descriptive statistics will be calculated on all pre-intervention patient variables across all accrued patients, by treatment group and by clinic to ensure that key patient characteristics related to the risk of CI or its diagnosis (i.e., age, sex, comorbidities) are balanced across treatment arms. Imbalanced patient characteristics will be considered for inclusion as covariates in the primary analyses.

For H1, we will fit a generalized LMM in which the binary post-index CI diagnosis outcome will be predicted via a link function from fixed effects for the clinic-randomized predictor, γ_{10} , and patient covariates, γ_{0*} , and a random clinic intercept, v_j , such as:

$$\text{logit}(\text{diagnosis}_{ji}) = \gamma_{00} + \gamma_{10}\text{CI-CDS}_j + \gamma_{0*}(\text{pt covars})_{ji} + [v_j].$$

Parameter γ_{10} is expected to be positive and statistically significant, indicating that accrued patients in clinics randomly assigned to CI-CDS are more likely to receive a CI diagnosis in the observation period than patients in UC clinics, accounting for fixed effects and random clinic variation.

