## 2.2 Randomization

Simple randomization will be carried out using SAS PROC PLAN to allocate clinics equally (1:1) to the CI-CDS (intervention) or UC (control) treatment arm. Because it is common for patients to see more than one clinician in a clinic location over time, and for clinicians within a clinic location to discuss aspects of care delivery with each other, the risk of intervention contamination within clinics is rather high. Randomizing by clinic rather than by PCC or patient will minimize risk of intervention contamination.

Each accrued patient will be assigned to the clinic in which his or her index visit takes place, and as such will be assigned to the treatment group to which their clinic was randomly assigned. Post-index visits may take place in the same or different clinics or treatment groups relative to

the index visit and may or may not be eligible for the CI-CDS to offer treatment recommendations. In keeping with an ITT principle, all index and post-index visits and outcome measures for each patient will be attributed to the treatment group assignment of the clinic where the index visit took place.

The nature of the intervention prevents study personnel, clinic leaders, or primary care clinicians from being blinded to the treatment group assignment of each clinic.

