## **2.3 Study Eligibility**

### **2.3.1 Primary Care Clinics**

HealthPartners leaders have agreed to enroll at least 30 primary care clinics from the Twin Cities metropolitan area into this clinic-randomized effectiveness trial. The co-PIs will collaborate with HealthPartners leaders to identify specific clinics to enroll with the intention that study clinics are representative of primary care environments at this and other health systems. Clinics will be excluded from participation for reasons such as:

- likely to close or transfer ownership during the study period;
- planned leadership or operational transitions during the study period;
- established CI workflow in place;
- resident training facility;
- involved in conflicting research;
- few patients  $\geq 65$  years of age;
- pilot location.

All potential study clinics are currently using a version of the CDS platform for non-CI-related clinical domains with high use rates.

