### **2.3.3 Patients**

The patient populations whose data will be included in the primary effectiveness analyses are the patients who have index visits at the CI-CDS and UC clinics during the accrual period. Patients will be automatically screened by the CI-CDS algorithms for intervention eligibility at all primary care visits at the randomized clinics during the intervention period. Patients who have a visit that meets the minimal intervention eligibility criteria during the accrual period will be considered accrued into the study.

Patients are accrued into the study upon completion of an index visit. The index visit is the first visit during the accrual period at which all of the following intervention eligibility criteria are met on the visit date:

- Primary care office visit at a randomized clinic during the accrual period, and
- Patient is age 65 or over, and
- Patient has no CI diagnosis documented in the EHR prior to the visit (ICD-10 codes F01-F03, G30, G31.0, G31.2, G31.83; or F06.7, G31.84), and
- Patient has elevated risk of CI
  - Any abnormal score on a comprehensive cognitive assessment (MoCA, MMSE, Mayo Mini Mental, or SLUMS) in the prior 18 months, or
  - MiniCog score <3 in the prior 18 months and there is no evidence of a subsequent comprehensive cognitive assessment (MoCA, MMSE, MMM, SLUMS), or
  - Risk of a dementia diagnosis in the next 3 years  $\geq 15\%$  as calculated by the algorithm developed in the R61 phase

Any of the following exclusion criteria will prevent a visit from being intervention eligible, and therefore not considered for index visit status:

- Patient has received active parenteral chemotherapy within the last year
- Patient has stage 4 or equivalent cancer diagnosis
- Patient is enrolled in hospice care or palliative care programs

All accrued patients who meet these minimal eligibility criteria, except those who have opted out of research participation, will be included in the ITT primary study analyses to maximize the generalizability of study results. As this is a pragmatic clinic-randomized trial, patients on exclusion lists will have been assessed for intervention eligibility, and the CI-CDS intervention may have been delivered during a visit to a randomized clinic. All data from each patient (e.g., outcome measures) will be attributed to the treatment group assignment of the clinic where the index visit took place.

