## 2.4 Study Measures and outcome definitions

### 2.4.1 H1 outcome (primary): CI detection

The primary study outcome is CI detection. CI detection will be a binary outcome calculated from EHR data that is present if an ICD-10 diagnostic code for CI (dementia or mild cognitive impairment [MCI]) is documented at an outpatient or inpatient encounter, or added to the problem list, between the index visit and the end of the observation period, inclusive. The diagnostic codes that will denote CI detection will be the same as those used in determining eligibility (section 2.3.3). The data elements needed to calculate this outcome will be extracted at the conclusion of the observation period from the EHR of patients in the ITT population. It is hypothesized that patients in CI-CDS clinics will be more likely to have CI detected than patients in UC clinics.

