## 6.0 SAMPLE SIZE AND POWER

The primary hypothesis test will compare patients in CI-CDS clinics to those in UC clinics on the likelihood that CI is diagnosed during the observation period. We conducted a power analysis to estimate the minimum detectable rate of new CI diagnoses given ranges of assumptions about

analytic sample sizes, proportions of patients currently meeting outcome criteria, and clinic intraclass correlation ( $ICC_{clin}$ ).

We used data accrued into the CI-CDS system during the R61 silent pilot to identify patients who met intervention eligibility criteria at clinic visits (section 2.3.3). Based on the pilot CI-CDS data, we estimated that, on average, about  $n=100$  patients in each of at least 30 clinics will likely have an index visit over the course of a 12-month accrual period.

An EHR-based cohort that consisted of patients who were age  $\geq 65$  and had a primary care visit between September 2021 and August 2022 was assembled to provide estimates of CI diagnosis rates in primary care clinics that were candidates for randomization. The proportion of patients who had at least one CI diagnosis code at an encounter or listed on their active problem list during the 12-month period was 2.3% among all patients in the cohort, and 15.1% among those who had a MiniCog $<3$  during the period. The power analysis will assume that 8-

16% of study accrued patients in UC clinics will have CI recognized between their index visit and end of their observation period.

There was substantial variation across primary care clinics in the proportion of patients with CI recognized as an encounter diagnosis or on their active problem list at the time of their 2021-2022 primary care visit. Among all patients,  $ICC_{clin}=0.03$ , and among those with MiniCog $<3$ ,  $ICC_{clin}=0.04$ . The power analysis will assume  $ICC_{clin}=0.03-0.05$ .

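### Optional precision gain: the H1 model has no clinic-level baseline diagnosis rate, although clinics are simply randomised and clinic variation supplies most of the unadjusted standard error

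*SAP*

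**What the plan says.** The H1 model in SAP 3.2 has "fixed effects for clinic-randomized treatment group and any patient covariates (e.g., age, sex, predicted risk score) and a random clinic intercept". Protocol 9.5.1 gives the same equation. Neither contains a clinic-level covariate, and in both the patient covariates are examples, not a closed list.

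On allocation, SAP 2.2 says "Simple randomization will be carried out using SAS PROC PLAN to allocate clinics equally (1:1", with no stratification or constraint at the primary site. SAP 2.3.1 says "HealthPartners leaders have agreed to enroll at least 30 primary care clinics"; the power table covers 30, 34 and 38.

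SAP 6.0 states: "There was substantial variation across primary care clinics in the proportion of patients with CI recognized". It gives a clinic ICC of 0.03 among all patients and 0.04 among those with a positive MiniCog. The source is a 2021-2022 EHR cohort that "was assembled to provide estimates of CI diagnosis rates in primary care clinics that were candidates for randomization".

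Elsewhere, pre-randomisation clinic characteristics appear only in reports to the DSMB (Protocol 7.3.2 and 7.4, SAP 4.3). The contextual factors in Protocol 9.5.2 are home-address measures for secondary interaction models.

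On imbalance, Protocol 9.5.1 says "Imbalanced patient characteristics will be considered for inclusion as covariates in the primary analyses"; SAP 3.1 reserves such adjustment for secondary analyses.

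**The concern.** With about 34 clusters and no balancing at randomisation, the arms can differ by chance in how readily their clinics diagnose CI. The random intercept allows for this honestly, by widening the standard error. A clinic's own diagnosis rate before randomisation is a direct way to explain some of that variation, and the plan does not use it. What is at stake is power, most of all if only the agreed minimum of 30 clinics is randomised. Validity is not at stake.

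**Working it through.** **1. The plan's own figure.** Inputs from SAP 6.0: 34 clinics, n=100 per clinic, ICC 0.04, 12% in usual care, two-sided alpha 0.05, power 0.80.

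- Design effect = 1 + 99 × 0.04 = 4.96.
- Effective N = 3400 / 4.96 = 685.5.
- The two-proportion formula with pooled variance gives a detectable rate of 19.81%, against the stated 19.8%. Power at 19.8% is 79.9%.
- With 30 clinics the detectable rate is 20.4% and power at 19.8% is 74.8%.

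**2. How much of the standard error is clinic variation.**

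- SD of true clinic rates = sqrt(0.04 × 0.12 × 0.88) = 6.50 points.
- SD of the chance arm difference in underlying clinic rates = 6.50 × sqrt(4/34) = 2.23 points, so 95% lie within ±4.4 points. The planned effect is 19.8 - 12 = 7.8 points.
- Adding binomial sampling of 100 patients per clinic gives a total standard error of 2.48 points.
- Share of variance due to clinics = 2.23² / 2.48² = 81%, before any patient covariate.

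**3. What a clinic baseline could recover.** Let r be the correlation between true pre-trial and trial-period clinic rates. The documents do not give it. As an idealised upper figure, with a noise-free baseline and no lost degree of freedom, the design effect becomes (1 - ICC) + n × ICC × (1 - r²). At r=0.5 this is 0.96 + 4 × 0.75 = 3.96, with a detectable rate of 18.9% and power of 88%.

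A more realistic simulation adds baseline sampling noise and the lost degree of freedom. Assumptions outside the documents: a 1% new-diagnosis rate at baseline, baseline ICC 0.01, and 1000 baseline patients per clinic. It regresses the clinic-level logit (0.5 added to both counts) on treatment, with or without the baseline logit. The t test has K-2 or K-3 degrees of freedom, and there are 40,000 runs per cell (Monte Carlo error about 0.2 points). Power is for 12% vs 19.8% at ICC 0.04:

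| Clinics | r | Without | With |
|---|---|---|---|
| 34 | 0 | 79.2% | 78.0% |
| 34 | 0.3 | 79.5% | 80.5% |
| 34 | 0.4 | 79.4% | 82.3% |
| 34 | 0.5 | 79.0% | 84.8% |
| 34 | 0.7 | 79.4% | 91.5% |
| 30 | 0 | 73.9% | 72.1% |
| 30 | 0.4 | 73.5% | 76.3% |
| 30 | 0.5 | 74.1% | 79.9% |

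Type I error is 4.8-5.0% with and without the term. Break-even is near r=0.25. Other assumed baselines (0.5% or 1%, ICC 0.005) give +4.5 to +4.8 points at r=0.5 with 34 clinics. Between 3% and 17% of clinics have no baseline event, depending on these assumptions, hence the 0.5 correction.

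**4. Allowing for patient covariates.** Suppose age, sex and risk score absorb a quarter or a half of the clinic variance (an assumption; residual ICC 0.03 or 0.02). Power at 34 clinics is then already 87% or 94%. The gain at r=0.5 falls to +4.3 or +1.9 points; at r=0 the change is -1.2 or -0.8.

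**5. The planned model form.** A random-intercept logistic model fitted by maximum likelihood (34 clinics, 4,000 runs, no patient covariates) shows the same pattern: r=0, 81.9 to 81.4%; r=0.3, 81.6 to 83.8%; r=0.5, 80.9 to 87.0%. Its Wald tests are slightly liberal either way: type I error is 6.1% without and 6.5% with the term at r=0, and 6.3% for both at r=0.5. The clinic-level figures are therefore the ones to rely on.

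**The case against.** The strongest reply is that this is a preference. The power calculation already divides N by the design effect and spans ICC 0.03-0.05, so the clinic variation in step 2 is priced in. That is right. A reader might infer from the missing term that the test is invalid, that chance imbalance biases the result, or that the trial is underpowered. The documents support none of these.

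The reply continues that nothing shows r to be above 0.25, and that the larger gains ignore the patient covariates the plan names as examples. Both points stand. With half the clinic variance absorbed, the gain at r=0.5 is about 2 points.

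A reader might also infer that the 2021-2022 clinic rates can simply be put into the model. They are a poor match. They count any CI code or active problem-list entry in all patients aged 65 or over, whereas H1 patients must satisfy "Patient has no CI diagnosis documented in the EHR prior to the visit" and be at elevated risk. A new-diagnosis rate is closer, but still covers a wider population than the accrued one. CI-CDS might also weaken the link between past and present rates in intervention clinics, which a single baseline slope does not capture.

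Lastly, a clinic term added to an open covariate list is not pre-specification. That stands, so the list has to be closed in the same edit.

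**Conclusion.** The point holds as an optional improvement in precision. The planned analysis accounts for clustering and the stated power figures are correct. One pre-fixed clinic baseline rate would cost about 1 point of power at 34 clinics, or just under 2 at 30, if it predicts nothing. It would gain about 5 to 6 points at r=0.5 before patient covariates, and about 2 to 4 once they absorb a half to a quarter of the clinic variance. At r=0.5 without patient covariates, 30 clinics would perform about like 34 unadjusted ones (detectable rate 20.4% down to about 19.8%). All gains rest on r and on the assumed baseline rate, ICC and clinic size, so no single figure should be quoted.

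The Protocol 9.5.1 wording on imbalanced characteristics is an editorial matter. A reader might take it as leaving the primary model undecided, but the later SAP 3.1 largely settles that such adjustment is secondary.

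**What to change.** In SAP 3.2, name one closed list of primary covariates: age, sex, MC-PLUS score at index, and the clinic's pre-randomisation rate of new CI diagnoses. Define that rate with the SAP 2.3.3 codes, in patients aged 65 or over with no earlier CI code, over one fixed window before randomisation, on the logit scale with 0.5 added to both counts. Keep the random clinic intercept. Decide on inclusion once, without checking correlations in trial data, and report the model without the clinic rate as a sensitivity analysis. The extra term slightly changes the conditional odds ratio, which is a further reason to fix it in advance.

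Timing: SAP 2.4.1 says "The data elements needed to calculate this outcome will be extracted at the conclusion of the observation period". The documents do not show whether that has happened; the change is sound only before it.

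Cost: a dated revision of an approved SAP in an unblinded trial, one clinic-level degree of freedom, and probably one further EHR extract.

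Editorial: align the Protocol 9.5.1 sentence on imbalanced characteristics with SAP 3.1.

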3.1 Inclusion Criteria

Patients are accrued into the study upon completion of an index visit. All of the following intervention eligibility criteria must be met on the visit date for the visit to be an index visit:

- Primary care office visit at a randomized clinic during the accrual period, and

Definitions

Intervention Period

- CI-CDS implementation date through a predetermined time at which the interface will be turned off in the intervention clinics

Accrual Period

- CI-CDS implementation date through a predetermined time at which no more people will be included in the analytic sample

Index Visit

- Varies by patient
- First visit during accrual period at which the CI-CDS identifies that the patient is study eligible
- Patient is accrued into study at index visit

Observation Period

- Varies by patient
- Index visit date through a predetermined time at which outcome data will no longer be accumulated

- Patient is age 65 or over, and
- Patient has no CI diagnosis documented in the EHR prior to the visit, and
- Patient has
 - Any abnormal score on a comprehensive cognitive assessment (MoCA, MMSE or SLUMS) in the prior 18 months, or
 - MiniCog score <3 in the prior 18 months and there is no evidence of a subsequent comprehensive cognitive assessment (MoCA, MMSE, SLUMS), or
 - No cognitive assessment in the past 18 months and risk of a dementia diagnosis in the next 3 years $\geq 15\%$ as calculated by the MC-PLUS algorithm developed in the R61 phase, and
- First visit during the accrual period at which all prior inclusion criteria are met.

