9.4 Outcomes

9.4.1 Primary outcome

The primary outcome will be CI detection (H1). CI detection will be a binary outcome calculated from EHR data and defined as occurring when an ICD-10 diagnostic code for CI is documented at outpatient or inpatient encounters, or added to the problem list, between the index visit date and the end of the observation period, inclusive.

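### The secondary H1 model's time covariate is computed from the outcome, so its time terms have no finite maximum-likelihood estimate under logit and only reflect the coding under log

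*SAP*

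**What the plan says.** SAP 3.2 tests H1 with a mixed model for a binary outcome: any CI diagnosis during observation, with a random clinic intercept. The logit form is displayed and a log link is also allowed. A secondary model then adds "time elapsed between the index visit and the first EHR-documented CI diagnosis, or zero for those lacking a CI diagnosis" and the interaction of that variable with treatment. The variable is expressed in years "so that it quantifies the predicted annual change in CI diagnosis rates", and the SAP states: "The time parameter is expected to be near zero and not statistically significant". If time to diagnosis differs by arm, "log (observation time) may be included as an offset in the primary analysis". Protocol 9.5.1 specifies the same model, coding, expectation and offset.

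Three other statements bear on this:

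- Protocol 9.4.1 counts diagnoses "between the index visit date and the end of the observation period, inclusive", so a diagnosis on the index day qualifies.
- Protocol 3.1 defines the observation period as "Index visit date through a predetermined time at which outcome data will no longer be accumulated".
- SAP 3.2 already plans to describe, by arm, "the time elapsed between study accrual and recognition".

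**The concern.** A predictor should be definable without knowing the outcome. This one is not: it is zero for everyone undiagnosed and, apart from index-day diagnoses, positive for everyone diagnosed. Zero also has two meanings, undiagnosed and diagnosed on the index day.

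The plan nevertheless gives the coefficient a substantive meaning and predicts its value. An analyst following the text could therefore publish a numerical artefact as a finding about timing. A diverged logit fit could be taken as confirming the prediction, and a log-link fit as a strong annual rise in diagnosis. Neither would inform the decision about the offset that follows in the same paragraph.

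**Working it through.** **Inputs.** The plan's median design (SAP 6.0) is 34 clinics of 100 patients, ICC 0.04, and 12% UC versus 19.8% CI-CDS. Follow-up is 12 to 24 months (Protocol 9.5.1). Assumptions not in the documents: follow-up uniform over that range; diagnosis time uniform within follow-up unless stated; diagnosis at least one day after index unless set to the index day.

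**The plan's own figure.** Effective N = 3400/(1 + 99 × 0.04) = 3400/4.96 = 685.5. A two-proportion calculation at 80% power and two-sided 0.05 returns 19.8%, as stated. All 27 cells of Table 1 agree within 0.1 percentage point. The scenario is sound and the power table is not in question.

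**Logit link, algebra.** Suppose no diagnosis falls on the index day, so each diagnosed patient has time ≥ 1/365. Set the intercept to −K, the time coefficient to 730K, and the other terms and the clinic SD to 0. Undiagnosed patients have linear predictor −K. Diagnosed patients have at least −K + 730K/365 = K. Hence −2 log-likelihood is at most 2 × 3400 × log(1 + e^(−K)), which is 45.7 at K = 5 and 0.31 at K = 10 and tends to 0. There is no finite maximum.

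If some diagnoses fall on the index day, raising the time coefficient still pushes the fitted probability of every later diagnosis toward 1 without affecting patients at time zero. The time terms still diverge. The arm coefficient stays finite, but it contrasts only index-day diagnosis with no diagnosis.

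**Logit link, numerical check.** −2 log-likelihood with a random clinic intercept, time coefficient fixed and the other parameters re-optimised. Each row is one simulated data set.

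| Time coefficient | 0 | 5 | 20 | 100 | 500 | 2,000 |
|---|---|---|---|---|---|---|
| No index-day diagnoses (211 UC, 276 CI-CDS diagnosed) | 1169 | 490 | 222 | 54 | 1.2 | 0.0 |
| About 20% index-day, assumed (187 and 305; 99 on index day) | 1678 | 1120 | 926 | 859 | 845 | 840 |

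What software prints depends on when it stops. In one fixed-effects logit fit the time coefficient was 266 (p<0.001) at 10 iterations, 6,091 (p=0.95) at 25 and 9,024 (p=0.998) at 100.

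**Log link, closed form.** Within an arm, let n0 be the number undiagnosed, T the longest time to diagnosis, and S the sum of (1 − t/T) over the diagnosed. The fixed-effects log-binomial maximum lies on the boundary, with

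slope = log((S + n0)/S)/T.

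This is positive whenever anyone is undiagnosed. Taking T at its documented maximum of 2 years and mean t = 0.75:

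- UC: 204 diagnosed, n0 = 1496, S = 204 × 0.625 = 127.5; slope = log(1623.5/127.5)/2 = 1.27.
- CI-CDS: 336.6 diagnosed, n0 = 1363.4, S = 210.4; slope = log(1573.8/210.4)/2 = 1.01.

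The longest observed time is usually below 2 years, which raises both figures.

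**Log link, simulation (500 trials each), mean slope per year.**

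| | Log-binomial UC / CI-CDS | Poisson-log UC / CI-CDS |
|---|---|---|
| Diagnosis unrelated to follow-up length | 1.38 / 1.07 | 2.38 / 2.00 |
| Constant diagnosis hazard | 1.37 / 1.08 | 2.33 / 1.98 |

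The slope hardly changes between the two situations it is meant to distinguish. Across sensitivity runs (8%, 12% or 16% in both arms; early, late or 20% index-day diagnosis) the lowest log-binomial slope in any trial was 0.85.

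**Interaction, Poisson-log with clinic-robust SE, 100 runs each.** It was significant in 77% of runs with identical timing but 12% versus 19.8% diagnosed. It was significant in 2% of runs with equal rates and faster diagnosis in CI-CDS. It follows the diagnosis rates, not timing.

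**A covariate that works.** Planned follow-up length in a logit model gave 0.00 and 0.73 log-odds per year (SE 0.16) in the two situations of the preceding table, with the arm SE unchanged at 0.21.

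**Offset.** With everyone observed to the fixed end date, adding it shifted the log odds ratio by 0.003 on average and 0.024 at most in 1,000 runs. Rejection without it and under the conditional rule was 78.3% and 78.2% when CI-CDS speeds diagnosis, and 5.0% and 4.9% at equal rates. The trigger here was an assumed t-test among the diagnosed. In separate runs (300 per setting) with observation time cut at death or leaving, equal loss of 5–15% per year gave mean shifts of 0.005–0.010. Unequal loss (assumed 5% versus 10% per year) gave 0.048, and rejection moved from 72% to 77%.

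**The case against.** The model is secondary, and Protocol 9.5.1 rests the effectiveness conclusion on the primary analysis. Under a log link the arm coefficient is reasonable: 0.55 log-binomial and 0.52 Poisson-log, against an actual log risk ratio of log(0.198/0.12) = 0.50. The descriptive summary already covers time to recognition. All of this stands and limits the reach of the point, but none of it gives the time terms a meaning. Neither document offers another coding, a person-period layout or a penalised fit that would.

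Four stronger readings are tempting and not supported:

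- That the primary H1 test or the power is compromised. The displayed primary model contains no time term, and Table 1 reproduces.
- That a logit fit will visibly fail. It may instead be reported as a result with p near 1, which is the more troublesome outcome.
- That the offset clause distorts the primary test. Its effect is negligible if observation time runs to the fixed end date, as both documents define it, or if loss is similar in both arms. On a log link such an offset is standard. The interaction may be the intended trigger, although the text names no test and the interaction does not measure timing.
- That removing the offset clause would fully pre-specify the primary model. The link and the patient covariates would still be open.

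**Conclusion.** The specification is wrong as written and should be fixed; the error is confined to the secondary model. The logit result follows from the definition of the covariate and needs only some diagnoses after the index day in each arm. It concerns maximum likelihood; a penalised or Bayesian fit would be finite, but none is planned.

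The log-link slopes of about 1.4 and 1.1 per year come from fixed-effects log-binomial fits without the planned clinic intercept, and their exact size depends on the assumed timing. Their sign and their insensitivity to follow-up dependence do not rest on one timing pattern: the sign follows from the closed form, and the slope was nearly the same with and without dependence on follow-up. Under neither link can the time term measure annual change in diagnosis, and the interaction cannot show whether timing differs by arm.

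The offset clause is a minor matter. It leaves an outcome-driven option in the primary analysis, usually with negligible numerical effect.

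**What to change.** In SAP 3.2 and Protocol 9.5.1, delete the elapsed-time covariate, its interaction with arm, the coding sentence and the expectation of a near-zero parameter. Rely on the by-arm description of time to recognition already in SAP 3.2. If a model is wanted, choose it by the question:

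- Does diagnosis depend on follow-up length? Use planned follow-up, (fixed end date − index date)/365, which is defined for every patient.
- Does timing differ by arm? Use a clinic-clustered time-to-first-diagnosis model and state how death, leaving the care system and index-day diagnoses are handled.

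Also delete the conditional offset sentence, which removes one choice driven by a post-randomisation outcome. Protocol 9.5.1 extends the same approach to the replication site, so the site-specific plan should not inherit the covariate.

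The cost is a few sentences in two documents. The first option needs only the index date and the fixed end date. The displayed primary model and the sample size do not change, and neither deletion nor the first option needs new data.
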